#### **5. Test Groups**

The trial was divided into 3 groups, 40 cases were to be collected in each group, totaling 120 cases.

1) Control group: gelatin sponge wrapped thrombin and tobramycin dexamethasone ophthalmic ointment group.

2) Test group A: temperature-sensitive hydroxybutyl chitosan (HBCS) group

3) Test group B: HBHS combined with 5-fluorouracil (5-FU) group

## 6. Treatment

With random table, the patients were randomly divided into three groups. In group A, HBCS was applied to the surface of the anastomosis of the nasal mucosal flap and the lacrimal sac mucosal flap. During the aforesaid procedure, 0.3 ml of 5-FU solution (25 mg/ml) was injected under the nasal mucosa around the anastomosis in group B. (Sup.1)

Anastomoses in Group C patients were covered with gelatin sponges encapsulated with thrombin, tobramycin dexamethasone, and oculentum.

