#### **4. Exit Criteria**

1) Patients who could not or did not undergo the procedure for various reasons, such as the occurrence of certain comorbidities, complications, or specific physiological changes in the subject that make continuation of the procedure inadvisable;

2) Patients whose surgical procedure was changed for various reasons.

3) Withdrawal of informed consent before the end of the study,

including:

a. Withdrawal from the study due to unsatisfactory efficacy or without any reason;

b. The occurrence of an adverse event or serious adverse event that, in the opinion of the physician, warrants termination of further clinical trials;

c. Poor compliance and inability to complete the review, resulting in incomplete information and affecting the determination of efficacy.

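### Allocation is described only as a random table, with no concealment and no time of assignment; if the arm is known before surgery is completed as planned, enrolment and exit can depend on it.

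*Combined protocol and SAP*

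**What the plan says.** Section 6 (Treatment) gives the whole method of allocation: "With random table, the patients were randomly divided into three groups". It does not mention how the sequence is restricted, who keeps it, how it is concealed, when the arm is assigned or who is blinded, and no other section does. The reference to Sup.1, which is not in the supplied text, follows the description of the group B injection, not the allocation sentence.

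Section 5 (Test Groups) fixes the sizes: "40 cases were to be collected in each group, totaling 120 cases".

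Discretion enters in two places. In section 3.2, exclusion 13 lets the investigator judge whether a patient's history could affect the results or raise the risk. In section 4 (Exit Criteria), exit 1 covers "Patients who could not or did not undergo the procedure for various reasons" and exit 2 covers "Patients whose surgical procedure was changed for various reasons". The rest of section 4 concerns withdrawal: 3a "Withdrawal from the study due to unsatisfactory efficacy or without any reason", 3b an adverse event that "in the opinion of the physician, warrants termination of further clinical trials", and 3c poor compliance or an incomplete review.

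Section 6 also shows where the arms part. HBCS goes on the anastomosis, 5-FU is injected around it, and the control sponge covers it. No step described before that point differs by arm.

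**The concern.** Randomisation protects the comparison only if nobody can act on the arm when deciding who enters or who stays. There are two routes by which that could fail here.

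- **Enrolment.** A recruiter who can read the next line of an open table can apply exclusion 13 differently according to what is coming. Patients turned away in this manner are never randomised, so analysis cannot bring them back.
- **Exit around surgery.** If the arm is known before the operation is completed as planned, exits 1 and 2 happen after randomisation, and a surgeon who knows the arm may decide them. Their stated grounds are open-ended.

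At stake is whether a difference in cure or effective rate can be put down to the study material. With 40 per arm, a few selective departures are enough to matter.

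**Working it through.** **What the documents settle**

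| Question | Answer in the documents |
|---|---|
| How the sequence is made | Random table (section 6); no restriction described |
| Who holds it and how it is hidden | Not stated |
| When the arm is assigned | Not stated |
| Where the arms first differ | At or around the anastomosis (section 6) |
| Who decides exclusion 13 | The investigator (section 3.2) |
| Who decides exits 1 and 2 | Not stated; reasons open-ended (section 4) |
| Which patients are analysed | No analysis set defined (section 10) |

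**The plan's own figures.** 3 × 40 = 120, as stated in section 5. 0.05/3 = 0.0167, as stated in section 10 for two-by-two comparisons. Both reproduce.

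**Illustration of size**

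Inputs from the documents: n = 40 per arm (section 5); pairwise threshold 0.0167, given alongside Fisher's exact test for the effective rate (section 10); chi-square for the cure rate, at 0.05 across groups (section 10).

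Assumed inputs: true cure p = 80% in every arm, which lies within the 58% to 94% range quoted in section 1; and k = 3 departures from one arm, all of them patients who would have failed. The documents give no exit rate, so k is a choice and not a limit.

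Formula: let S1 and S2 be independent Binomial(40, p). The affected arm is observed with S1 successes and max(0, 40 − S1 − k) failures. The other arm has S2 successes and 40 − S2 failures. The false-positive rate is the sum of P(S1)·P(S2) over all pairs whose test gives P below the threshold. The chi-square is uncorrected.

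| Test | No exits | 3 would-be failures leave one arm |
|---|---|---|
| Fisher, two arms, 0.0167 | 0.8% | 6.3% |
| Chi-square, two arms, 0.0167 | 1.5% | 7.4% |
| Fisher, two arms, 0.05 | 2.8% | 12.0% |
| Chi-square, two arms, 0.05 | 5.1% | 15.7% |

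The first two rows use the plan's pairwise threshold and are the relevant ones. The 0.05 rows are shown only because a reader might reach for that level; it is not the plan's criterion for pairs.

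**The other extreme.** Suppose 3 patients leave one arm for reasons unrelated to outcome. The affected arm is then Binomial(37, 0.8). The two-arm chi-square rate at 0.05 is 5.2%, against 5.1% with no exits, so there is essentially no inflation.

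Any real effect of 3 such exits lies between these two cases. The documents do not say where.

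**The case against.** The strongest reply is that the harm through exits 1 and 2 is conditional and may not arise. Those exits occur before or during surgery, and they can depend on the arm only if the arm is already known. If patients were assigned once the anastomosis was formed, most of these exits came first. Outcome is judged up to 6 months later, so a surgeon would need near-perfect foresight to remove only future failures. This stands: the illustration is an extreme case, not an estimate.

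Three stronger readings are tempting, and the documents do not support them.

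- A reader might infer that the arm did influence who stayed. Nothing shows this. The time of assignment is missing, not stated to be early.
- A reader might infer that exits damage the comparison beyond repair. That is true of selective enrolment. Patients who exit after assignment can often still be followed and analysed in their arm, and section 4 does not say they are dropped from analysis.
- A reader might take the random table to mean simple randomisation and expect badly unequal arms. Section 5 fixes 40 per group, which points to restricted allocation. A random table can produce that, and unequal arms would not in themselves bias the comparison.

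It can also be said that in-theatre opening is one valid option among several. Concealed assignment before surgery, with all assigned patients analysed, is another. That stands too. Late opening is preferred here because, on the description in section 6, earlier assignment brings no stated benefit. That description is brief and points to a supplement that was not supplied.

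What remains is that no text excludes foreknowledge of the arm, while the plan leaves discretion to people who may have it.

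**Conclusion.** The concern holds as a conditional risk. Allocation rests on one sentence, with no concealment and no time of assignment, while exclusion 13 and exits 1 and 2 leave room for judgement by people who may know the arm. If the arm is known before the operation is completed as planned, enrolment and exit can depend on it.

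The size cannot be derived from the documents. At 80% true cure, with 3 would-be failures leaving one arm of 40, pairwise error at the plan's threshold becomes roughly eight times its nominal-case value with Fisher (6.3/0.8 ≈ 7.9) and five times with chi-square (7.4/1.5 ≈ 4.9). These figures rest on an assumed cure rate, an assumed number of exits, perfect selection of failures, and analysis of only those who remain. The change should be made, because it is cheap and closes the gap at its source.

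**What to change.** Replace the allocation sentence in section 6 with a statement of four things:

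1. **Sequence.** A computer-generated 1:1:1 list in permuted blocks of mixed size (for example 3, 6 and 9), prepared by existing staff who neither enrol nor operate.
2. **Concealment.** Sequentially numbered, opaque, sealed envelopes.
3. **Time of assignment.** Each envelope is opened in theatre once eligibility is final and the anastomosis has been formed, since the arms in section 6 differ only from that point.
4. **Who counts as randomised.** Patients whose operation is not done or is changed before opening are listed as screened and not randomised. Everyone randomised is kept and analysed in the assigned arm.

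Late opening does not deal with changes made after the envelope is opened, or with exits 3a to 3c, which come later and relate to efficacy, adverse events or incomplete review. Those exits should be reported by arm and reason.

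If enrolment has already taken place, the sponsor should state how and when patients were actually assigned, and list all exits by arm, timing and reason.

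The cost is one list and 120 envelopes. The real downside is practical: all three study materials must be on hand in theatre for every case.

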## 7. Study Endpoint

The end of 6 months after surgery was used as the study endpoint.

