## **2. Aims:**

To investigate the effects of HBCS with and without 5-FU during Endo-DCR.

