## **10. Statistical methods**

To compare the differences between the adjuvant therapeutic effects of different En-DCR in the three groups: data were analyzed using SPSS 19.0 software, one-way ANOVA was used for age comparison, and Kruskal-Wallis H-test was used for comparison of postoperative comfort and blood leakage. Comparison of gender, complications, and cure rate

was performed by chi-square test, and the difference was considered statistically significant at  $P<0.05$ . Effective rate was compared by Fisher's exact probability method, and  $P<0.05$  was regarded as statistically significant difference, and  $P<0.0167$  was regarded as statistically significant difference for two-by-two comparison. The collected conjunctival sac and nasal flora were analyzed: alpha diversity analysis, PCA analysis, taxonomic composition analysis, and Lefse analysis were used, and differences were considered statistically significant at  $P<0.05$ . Comparisons between groups were made using chi-square test or fisher's exact probability method for adverse events and serious adverse events when necessary.

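### No primary outcome is named: section 7 gives only a time point, and section 10 tests two undefined efficacy rates, each at 0.05, so either can carry the efficacy claim

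*Combined protocol and SAP*

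**What the plan says.** All references are to the combined protocol and SAP.

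- **Section 2 (Aims)** is general: "To investigate the effects of HBCS with and without 5-FU during Endo-DCR". It names no outcome.
- **Section 7 (Study Endpoint)** is one sentence: "The end of 6 months after surgery was used as the study endpoint".
- **Section 10 (Statistical methods)** puts cure rate in a chi-square list, "Comparison of gender, complications, and cure rate", at P<0.05. It then says "Effective rate was compared by Fisher's exact probability method", also at P<0.05, and adds that P<0.0167 "was regarded as statistically significant difference for two-by-two comparison". It also provides for comfort and bleeding ("Kruskal-Wallis H-test was used for comparison of postoperative comfort and blood leakage"), for flora ("alpha diversity analysis, PCA analysis, taxonomic composition analysis, and Lefse analysis were used"), and for group comparisons "for adverse events and serious adverse events when necessary".
- **Section 8 (follow-up schedule)** places comfort and bleeding on day 1 only and flora sampling no later than week 8. Symptoms (tearing and discharge) and endoscopy are the only assessments at the last visit. That visit has a lower limit of 24 weeks and no upper one, while the visits from week 1 to week 12 carry plus-or-minus windows.
- **Section 9(c)** provides for treating granulation, scarring or adhesion at the anastomosis during follow-up.

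No section calls an outcome primary or secondary, defines either rate, or ties either rate to a visit.

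**The concern.** Cure and effective rate are two readings of the same question: did the operation work? With no primary named, a significant result on either could be reported as the trial's efficacy finding. Each test is run at 5%, so the chance of at least one false finding is above 5%.

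The missing definitions add freedom that no significance level controls. Nothing says which symptom and endoscopy findings make a patient cured or merely improved. Nothing says how a patient treated under section 9(c) is classified. This second gap bears directly on efficacy, because section 9 itself attributes most late failures to tissue overgrowth, scarring and blockage of the anastomosis. With 40 patients per group, reclassifying one patient moves a group's rate by 1/40 = 2.5 percentage points.

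**Working it through.** **1. The plan's own figure.** Three groups give three pairs, and 0.05/3 = 0.0167. The stated pairwise level is reproduced as a Bonferroni correction for pairs of groups. A correction that also covered two rates would be 0.05/6 = 0.0083, so the second rate is not allowed for.

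**2. Which outcomes are open at six months.** Set section 10 against section 8:
- Comfort and bleeding are assessed on day 1 only.
- Flora samples stop at week 8.
- Symptoms and endoscopy are assessed at the last visit.

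The efficacy choice at six months is therefore between cure rate and effective rate.

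**3. Bounds for two tests at 0.05.**
- Upper bound: 0.05 + 0.05 = 0.10.
- If independent: 1 − 0.95² = 0.0975.

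**4. Allowing for the overlap between the rates.** The documents define neither rate, so this step assumes that effective = cured + improved, which makes the cured a subset of the effective. The other inputs are:
- 3 × 40 patients (section 5);
- a three-group chi-square test for cure and a three-group exact Fisher test for effective, both at 0.05 (section 10);
- no true difference between groups;
- assumed rates. The only rate in the documents is the 58% to 94% success range in section 1, which is itself not defined.

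Results from 2,000,000 simulated trials per row:

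| Cure / effective | Cure significant | Effective significant | At least one | Exactly one |
|---|---|---|---|---|
| 60% / 85% | 0.051 | 0.043 | 0.086 | 0.078 |
| 70% / 90% | 0.050 | 0.041 | 0.084 | 0.077 |
| 80% / 94% | 0.049 | 0.033 | 0.075 | 0.069 |

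Check on the first row: both significant = 0.086 − 0.078 = 0.008, and 0.051 + 0.043 − 0.008 = 0.086.

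The last two columns show why the choice of rate matters. Among trials with any false positive, the two rates disagree in 0.078/0.086 = 91%, 0.077/0.084 = 92% and 0.069/0.075 = 92%.

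**5. Sensitivity to the assumed rates.** The grid took cure from 50% to 90%, with effective 2 to 30 points higher and at most 95%, and 400,000 trials per point. The chance of at least one false positive ran from 0.061 (at 70/72% and 90/92%) to 0.091 (at 50/80%).

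**6. After the fix.** With one rate primary, the false-positive chance is that of its own test in the table: 0.049 to 0.051 for cure by chi-square, or 0.033 to 0.043 for effective by Fisher.

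**The case against.** The strongest reply is that the problem is small and narrower than section 10 makes it look. Much of that is right.

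- **The list of outcomes.** A reader might infer that comfort, blood leakage and flora all compete for the main result. The schedule rules them out as six-month outcomes, so only the two rates are in play.
- **The size.** The inflation is modest and rests on an assumed relation between the rates. It concerns the three-group tests only. A claim that a particular treatment beats control also needs a pairwise result, and that error rate was not calculated. This stands as a limit on the figure. It does not remove the defect, because the figure takes both rates as fixed and leaves out the freedom in their definitions.
- **The last visit.** A reader might infer that an open-ended visit biases the comparison. Nothing in the documents shows that timing differs between groups. Section 7 can also be read as closing follow-up at six months, which would supply the missing limit. Nor is the lower limit at fault: six months is about 26.1 weeks, so a visit after 24 weeks includes it. What remains is an ambiguity to clear up.
- **Patients treated under section 9(c).** A reader might infer that their classification would overturn the result. The documents give no expected counts, so only the missing rule can be criticised.
- **Clinical convention.** It may be said that success is obvious to a lacrimal surgeon. The plan itself tests two different success rates, so it does not rest on one shared meaning.

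**Conclusion.** The concern holds. The plan fixes when efficacy is judged but not what is judged, and its two undefined efficacy rates each receive the full 0.05. The chance of at least one falsely significant three-group test is about 7.5% to 8.6% at the three assumed pairs of rates, about 6% to 9% over the wider grid, and at most about 10%. The bound of about 10% does not depend on how the rates overlap; the narrower ranges assume that cured patients are a subset of effective ones.

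This should be corrected, though the inflation is not large. The documents do not show that a result was selected after the fact or that visit timing favours a group. Whether 40 per group is enough is a separate question: no effect size or power is stated, and this point does not settle it.

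**What to change.** Before the groups are compared:

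1. **Section 7:** name either cure rate or effective rate as the single primary outcome at six months. The choice is the sponsor's.
2. **Definition:** state which symptom and endoscopy findings at the last visit count as success, and how patients treated under section 9(c) are counted in the analysis. This concerns counting only, not their treatment.
3. **Section 10:** test the primary across the three groups at 0.05 and its pairs at the plan's 0.0167, and say that this pairwise level applies to the chosen primary.
4. **Other outcomes:** label the other rate secondary; comfort, blood leakage and flora secondary or exploratory; complications and adverse events safety.
5. **Minor clarification:** reconcile sections 7 and 8 by giving the last visit an upper limit. Its width is the sponsor's choice.

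**Cost.** The change is wording in sections 7, 8 and 10, with no added visits or tests. A positive result on the other rate could no longer be presented as the main finding. If the pairwise tests are made conditional on a significant three-group test, that is a rule section 10 does not now contain. With three groups it is slightly conservative when combined with 0.0167, and it should be stated as an addition.

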## 8. Flow-up

		1 day	1 week (±1 day)	2 weeks (±1 day)	4 weeks (±3 days)	8 weeks (±3 days)	12 weeks (±7 days)	>24 weeks
Subjective perception	Comfort	√						
	Bleeding	√						
	Epiphora, mucopurulent discharge	√	√	√	√	√	√	√
Specimen collection	conjunctival sac		√	√	√	√		
	nasal cavity				√			
Endoscope						√	√	√

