## 9. Expected Risks and Measures to Address Them

1) En-DCR is an invasive procedure and there is a risk of blood leakage from the lacrimal sac-nasal anastomosis in the early postoperative period.

Most of the distant cases fail due to mucosal epithelial tissue hyperplasia, scarring and obstruction of the anastomosis. HBCS can stop diffuse bleeding, inhibit bacteria, and promote wound healing, etc. 5-FU can effectively inhibit the proliferation of fibroblasts. However, the effect of the two as dressings at the anastomosis of the lacrimal sac and nasal mucosa applied to En-DCR is uncertain. We will take appropriate measures if the following situations occur.

- a. Localized infection: intensive anti-infection treatment.
- b. Severe postoperative bleeding: Use other drugs and dressings to stop bleeding.
- c. Granulation tissue, scar proliferation and anastomotic adhesion: excise or separate them, and apply antiproliferative drugs to the wound.
- d. Delayed healing: use other dressings and medications.

2) Adequate and repeated education, obtaining informed consent, establishing timely and effective communication with patients, and standardized follow-up.

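### Does the open-ended last visit (more than 24 weeks) leave the 6-month endpoint without a usable definition?

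*Combined protocol and SAP*

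**What the plan says.** Section 7 sets the time point in one sentence: "The end of 6 months after surgery was used as the study endpoint". It gives no tolerance.

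The table in section 8 puts a two-sided window on each of the five visits from 1 week to 12 weeks; the last of these is headed "12 weeks (±7 days)". The final column is headed only as more than 24 weeks. Symptoms (epiphora, mucopurulent discharge) and endoscopy are both ticked at 8 weeks, at 12 weeks and at this final visit.

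Section 10 assigns a chi-square test under "Comparison of gender, complications, and cure rate", and says that "Effective rate was compared by Fisher's exact probability method". Neither rate is tied to a visit.

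On allocation, section 6 says: "With random table, the patients were randomly divided into three groups".

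**The concern.** The interim visits have tolerances, and the visit that supplies the endpoint has none. Read literally, the final column accepts an assessment on day 169, before 6 calendar months have passed, and equally one at 9 or 12 months. Because symptoms and endoscopy are recorded together at three visits, section 10 taken alone would allow cure rate to be scored at any of them.

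Two things could be at stake. First, the published figure might be called a 6-month rate while mixing assessments made at different times. Second, if one group tended to be seen later than the others and outcomes change after 6 months, the comparison between groups would be biased. An open-ended visit also never becomes overdue, so the plan sets no date after which a patient not yet seen counts as missing.

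**Working it through.** **Does the text leave the visit open?**

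- Section 7 fixes the time at 6 months.
- The 8- and 12-week visits in section 8 end by day 59 (8 × 7 + 3) and day 91 (12 × 7 + 7). Neither can be a 6-month assessment.
- One visit remains. Scoring the rates at 8 or 12 weeks would contradict section 7.

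The missing pieces are therefore an upper tolerance and an explicit cross-reference from section 10.

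**How early can the visit be?** 24 weeks is 24 × 7 = 168 days, so the first admissible day is 169. Six calendar months is 365.25 / 2 = 182.6 days, and 182.6 − 169 = 13.6 days. This shortfall exists only if 6 months means calendar months. The later visits are at 4, 8 and 12 weeks and then beyond 24; counted in 4-week months, 24 weeks is 6 months, and the heading reads as at least 6 months of follow-up.

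**How much could late visits matter?** The documents give no cure rate at 6 months, no rate of change afterwards and no distribution of visit times. The following inputs are assumptions, except the group size of 40 (section 5): cure p = 0.85 at 6 months; net loss h = 0.5%, 1% or 2% per month; a share f = 20% or 40% seen m months late.

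Shift in the rate = p × f × (1 − (1 − h)^m), in percentage points:

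| h per month | m = 3, f = 20% / 40% | m = 6, f = 20% / 40% |
|---|---|---|
| 0.5% | 0.25 / 0.51 | 0.50 / 1.01 |
| 1% | 0.50 / 1.01 | 0.99 / 1.99 |
| 2% | 1.00 / 2.00 | 1.94 / 3.88 |

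If the net change were instead a gain of 0.5% to 2% per month among the 15% not cured, the 6-month-late shift would be upward, by 0.09 to 0.68 points.

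For scale, the single-group 95% half-width is 1.96 × √(0.85 × 0.15 / 40) = 11.1 points. The half-width for a difference between two groups is 1.96 × √(2 × 0.85 × 0.15 / 40) = 15.6 points.

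**False-positive rate.** This is the three-group Pearson chi-square test at 0.05, with all 41³ tables enumerated. It applies to cure rate; Fisher's test for effective rate was not enumerated.

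| Timing | Rejection rate |
|---|---|
| No delay | 4.65% |
| All groups, 20-40% seen 6 months late | 4.67% to 4.81% |
| One group only, 20-40% seen 3 months late | 4.66% to 5.25% |
| One group only, 40% seen 6 months late, h = 2% (extreme corner) | 6.9% |

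The second row is what randomisation leads one to expect. The last two need timing that differs by group, which nothing in the documents suggests.

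**What would a written window change?** Take 24 to 28 weeks, that is days 168 to 196. It opens one day before day 169, so it does nothing about early visits. If patients seen after it stay in the main analysis, the same lateness gives the same shift as in the first table. If they are left out, precision falls: with 36 or 32 per group the between-group half-width rises from 15.6 to 16.5 or 17.5 points, and a selection effect becomes possible.

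**The case for a change.** The strongest argument for a change is that it is cheap and that the omission falls on the visit that matters most. A column heading and a sentence or two in section 10 would close the gap. Without them, a reader of the plan cannot tell whether the result is a 6-month rate or whether timing was alike across groups. Section 9 attributes most distant failures to tissue overgrowth and scarring; if distant means late, the plan itself treats outcome as dependent on time. The 6.9% corner shows that strongly unequal timing would not be harmless.

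Part of this stands. The heading is open-ended, and the link from section 10 is not written down. Reporting time from surgery to assessment by group would be good practice, and it needs only recorded visit dates.

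The rest does not carry the point to an amendment. The 6.9% requires a 6-month delay in 40% of a single group and the steepest assumed loss, none of it drawn from the documents. Two other passages that might be cited do not bear on visit windows. Section 4 lists "Poor compliance and inability to complete the review, resulting in incomplete information and affecting the determination of efficacy", but under withdrawal of consent and without saying what the review is. Section 9 speaks of "establishing timely and effective communication with patients, and standardized follow-up", which closes a sentence on patient education and consent as risk measures. That neither rate is defined is a separate matter and adds nothing to a point about timing.

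**Conclusion.** No change to the plan is needed. This is a missing detail that analysts would fill sensibly: section 7 gives the time point, one visit can supply it, and the comparison is between randomised groups. Followed as written, the plan still gives a sound three-group comparison.

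Under the assumed inputs, lateness shared by all groups moves the reported rate by at most 3.9 points and leaves the false-positive rate below 5%. The exposure is to the label of the rate as a 6-month figure more than to the test. This conclusion rests on visit timing being similar across groups, which randomisation makes the default but which the documents do not demonstrate. The sizes are illustrations only; the documents support no estimate of actual bias. A written window would not reduce the shift unless it changed attendance or removed patients, and removing them has its own cost.
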